## List of Abbreviations

AE	Adverse Event
AOIs	Area of interests
Bayley-III	Bayley Scales of Infant and Toddler Development 3 rd Edition
BB-12	Bifidobacterium animalis subsp. lactis
BERA	Brainstem Evoked Response Audiometry
BMI	Body mass index
CI	Confidence interval
DHA	Docosahexaenoic acid
DSMC	Data Safety Monitoring Board
EPA	Eicosapentaenoic acid
FAs	Fatty acids
HOME	The Home Observation for Measurement of the Environment
ICC	Intraclass Correlation Coefficient
IOWA	Infant Orienting with Attention
IPCW	Inverse Probability of Censoring Weighting
ITT	Intention-To-Treat
LGG	Lactobacillus rhamnosus GG
LMICs	Low- and middle-income countries
MRI	Magnetic Resonance Imaging
SAE	Serious Adverse Event
SCFAs	Short-chain fatty acids
SD	Standard deviation
SP	Study Physician
VPC	Visual Paired Comparison

## 1. ADMINISTRATIVE INFORMATION

Protocol: 0071/UN2.F1/ETIK/2018 (v14122021)  
ClinicalTrials.gov register Identifier: NCT03851120

### 1.1 Document Version History

Version Date	Version	Author	Signature	Change Description	Reason/Comment
08/18/2025	1.0	RA		Initial release.	Not applicable.

## 2. STUDY SYNOPSIS

Interventions are urgently needed to enhance early-life brain and cognitive development, especially in low- and middle-income countries (LMICs) where multiple biomedical and psychosocial risks prevail. It is estimated that 36.8% of young children in LMICs perform poorly in at least one developmental domain, Failure during this critical window of opportunity affects well-being into adulthood. While nurturing care and stimulation are known to enhance early-life brain development, the multiplicity of factors that influence brain development from conception onward suggests additional interventions may remain unknown.

The gut-brain axis has emerged as a promising avenue for potentially enhancing brain development. In infants, postnatal brain development parallels the maturation of gut microbiota, which suggests a potential role in development. Moreover, supplementation of pregnant women with probiotics has demonstrated long-term benefits to infants, including reduced infant allergies, which could be mediated by regulatory T cells that may also affect brain development. As such, supplementation during the prenatal period may provide other significant benefits. Other dietary components may enhance microbiome, such as omega-3 fatty acids (FAs). Indeed, both probiotics and omega-3 fatty acids are among the most studied dietary interventions regarding the gut microbiota, its response to challenge, the influence of the local immune cells, and the regulation of the short-chain fatty acids (SCFA) production.

The maternal gut microbiota may affect fetal neurodevelopment through transplacental transport of microbiota-derived metabolites like SCFA and compounds like lipopolysaccharides. Microbial metabolites and compounds can travel from the intestinal lumen to the bloodstream and the fetus via the placenta, providing biochemical signals that influence in-utero fetal neurodevelopment. A recent study in mice identified a connection between the maternal gut and fetal brain development through embryonic SCFA receptors, where SCFA from maternal gut microbiota were sensed by GPR41 and GPR43 in the sympathetic nerve of the embryo. Although evidence is still limited, a systematic review of probiotic interventions on cognitive development identified one randomized trial in which *Lactobacillus rhamnosus* GG was given to the mothers for 4 weeks before delivery and continued for six months postpartum either to the mother (if breastfeeding) or to the child (if not). The study showed a lower incidence of ADHD and Asperger syndrome at 13 years of age in the intervention group. These findings suggest that microbes and their metabolites in the maternal gut can affect fetal brain development and function in utero.

Both probiotics and omega-3 FAs could improve maternal gut microbiota diversity and demonstrate anti-inflammatory effects. Omega-3 FAs potentially synergize with probiotics to improve maternal microbiota composition by increasing SCFA production and supporting the growth of LPS-suppressing bacteria, such as *Bifidobacteria*. Thus, a combined supplementation may be more effective than either intervention alone. Along with their influence on the intestine, maternal probiotics and omega-3 FAs supplementation may increase breast milk DHA levels and establish a healthier microbiota in breast milk, thereby supporting infant postnatal brain development.

While there is some evidence that maternal probiotics and omega-3 FAs supplementation could support early-life brain development, few trials have explored the effects of these interventions, especially their combined impact. Previous research may not have adequately evaluated the effects of probiotic strains on neurodevelopment and may have overlooked socioenvironmental factors that could confound the results. Moreover, studies on maternal supplementation during pregnancy have not assessed the effect on fetal brain development, which is necessary to better understand the connection between prenatal and postnatal outcomes. The Brain Probiotic and LC-PUFA Intervention for Optimum Early Life (BRAVE) is a double-blind randomized controlled trial in Jakarta, Indonesia, aiming to evaluate the impact and safety of supplementation of healthy pregnant women with the combination of probiotics and omega-3 FAs from the second trimester

up to 6 months postpartum on fetal brain growth and infant development at the age of 4 and 6 months. This statistical analysis plan outlines the methodology for analyzing fetal brain development and infant development.

## 2.1. Primary Objective

The overall objective of this analysis is to examine the effect of maternal probiotics and higher-dose omega-3 FAs supplementation, supported with government program supplements, healthy eating, and psychosocial stimulation, during pregnancy through 6 months postpartum on fetal brain growth assessed by magnetic resonance imaging (MRI) and infant development at the age of 4–6 months assessed using brainstem evoked response audiometry (BERA), Bayley Scales of Infant and Toddler Development 3rd Edition (Bayley-III), and eye-tracking assessments.

The hypotheses of the primary objectives are:

**H1:** Compared to the control group, fetus of women who receive daily probiotics and higher-dose omega-3 FAs supplements will show higher whole brain volume at 36–38 weeks of gestational age.

**H2:** Compared to the control group, fetus of women who receive daily probiotics and higher-dose omega-3 FAs supplements will show higher myelination index at 36–38 weeks of gestational age.

**H3:** Compared to the control group, children of women who receive daily probiotics and higher-dose omega-3 FAs supplements will show higher cognitive and cognitive composite scores of Bayley-III at the age of 4–6 months.

**H4:** Compared to the control group, children of women who receive daily probiotics and higher-dose omega-3 FAs supplements will show patterns of BERA indicators suggestive of better auditory function at the age of 4–6 months, specifically:

- Lower absolute latencies for wave I, wave III, and wave V
- Lower interpeak latencies for wave I–III interval, wave III–V interval, and wave I–V interval (central conduction time).

**H5:** Compared to the control group, children of women who receive daily probiotics and higher-dose omega-3 FAs supplements will show patterns of Infant Orienting with Attention (IOWA) task indicators suggestive of better attention at the age of 6 months, specifically:

- Lower mean latency
- Lower task error

**H6:** Compared to the control group, children of women who receive daily probiotics and higher-dose omega-3 FAs supplements will show patterns of Visual Paired Comparison (VPC) task indicators suggestive of better memory at the age of 6 months, specifically:

- Higher novelty preference score
- Lower mean familiarization fixation

## 2.2. Secondary Objectives

The hypotheses of secondary objectives are:

- Compared to the control group, fetus of women who receive daily probiotics and higher-dose omega-3 FAs supplements will show higher cerebrum, white matter, deep gray matter, cerebellum, and brainstem volumes at 36–38 weeks of gestational age.
- Compared to the control group, children of women who receive daily probiotics and higher-dose omega-3 FAs supplements will show higher receptive language, expressive language, language composite scores, fine motor, gross motor, and motor composite scores of Bayley-III at the age of 4–6 months.
- Compared to the control group, children of women who receive daily probiotics and higher-dose omega-3 FAs supplements will show higher cue facilitation and lower cue interference assessed by the IOWA task at the age of 4–6 months.
- The intervention effects on each outcome will differ by specific subgroups, including child sex, birth order, maternal pre-pregnancy body mass index (BMI) status, maternal anemia, maternal age, maternal education, socioeconomic status, and home environment.

### 2.3. Study Population

The Brave study was a parallel, individually randomized controlled trial (1:1 allocation ratio) that was carried out in Jakarta, Indonesia, from 2019 to 2022 by the Department of Nutrition, Faculty of Medicine, Universitas Indonesia–[name] General Hospital and the Human Nutrition Research Center, Indonesian Medical Education and Research Institute (HNRC-IMERI), Faculty of Medicine, Universitas Indonesia. The primary objective of this study is to investigate how maternal probiotics combined with omega-3 FAs supported with government program supplements, healthy eating, and psychosocial stimulation could affect fetal brain development and later child brain functions and cognitive development at 4–6 months of age.

We screened potential participants through a patient listing from the maternal and child health unit in the local community health care and clinics. We recruited pregnant mothers in the first or second trimester of pregnancy at seven primary health centers in four municipalities in Jakarta.

Inclusion criteria of the trial:

- Indonesian pregnant women in the 2nd trimester of gestational period
- Healthy pregnancy (as measured by hemoglobin level, pregnancy status, pregnancy history)
- Having normal blood pressure
- Planning to stay in the study area until the child is 6 months old
- Willing to sign informed consent
- Having a legally acceptable representative who is capable of understanding the informed consent document and providing consent on the subject's behalf

Exclusion criteria of the trial:

- Having foreign objects in the body due to trauma, artificial heart valves, metal objects or ferromagnetic (plate, screw, clip, prosthetic), and electronic devices (pacemaker, cochlear implant, insulin pump), and being claustrophobic
- Having a history of previous gestational diabetes or having been diagnosed with gestational diabetes
- Having a history of type 1 and type 2 diabetes
- Severe anemia

## 2.4. Intervention

Provide a brief description of the details of each intervention being assessed including any potential control arm. If applicable, describe study drugs with dosages. Also include details of incomplete administration of study intervention e.g. acceptable reduction in study treatment for toxicity (where applicable).

Eligible pregnant mothers were randomly assigned to two groups (n=157 each):

(1) **Intervention group** consuming daily supplements of one capsule containing multistrain probiotics [Chr. Hansen A/S, Hørsholm, Denmark; *Lactobacillus rhamnosus* GG (LGG), *Bifidobacterium animalis subsp. lactis* (BB-12), *L. acidophilus* (LA-5)] and two capsules of higher-dose omega-3 FAs [Blackmores Pty Ltd, Australia; 720 mg eicosapentaenoic acid (EPA), 480 mg docosahexaenoic acid (DHA) in total], or

(2) **Control group** consuming one placebo capsule of probiotics (Chr. Hansen A/S, Hørsholm, Denmark) and two capsules of standard-dose omega-3 FAs (Blackmores Pty Ltd, Australia; 360 mg EPA, 240 mg DHA in total).

Both groups consumed the supplements from the 2nd trimester of pregnancy until 6-months postpartum, regardless of their breastfeeding status. Omega-3 FAs supplementation began at 22 weeks of pregnancy, while probiotics/placebo supplementation started at 26 weeks. The gestational age for all subjects was assessed using ultrasonography at the nearest community health center or [name] General Hospital by trained general practitioners. These start times were chosen due to the late recognition of pregnancy in our population and therefore to ensure uniform initiation for all participants. Additionally, probiotics/placebo supplementation commenced during the third trimester because of limited evidence regarding probiotics use in pregnancy before this period. The placebo probiotics capsules were indistinguishable from the active capsules in appearance, taste, and odor. Likewise, the omega-3 capsules appeared identical across groups. All mothers in both groups also received psychosocial stimulation and healthy eating modules. These modules were delivered once during pregnancy (at 30–34 weeks of gestation) and twice during postpartum (between 0–1 month and between 1–2 months after birth). In the study sample, the majority of infants were breastfed, thus likely receiving DHA via their mother's breastmilk in addition to their prenatal exposure. Outcomes assessments were performed at 36–38 weeks of gestational age for fetal brain volume and when children reached the age of 4–6 months for Bayley-III, BERA, and eye-tracking assessments. All participants, outcome assessors, and field and research teams were blinded to the allocation of the intervention.

## 2.5. Randomisation and Blinding

Randomization was stratified by maternal educational status ( $\geq 9$  years vs.  $< 9$  years of education) and municipality economic status (high economic areas in South and Central Jakarta vs. low economic areas in North and East Jakarta), using block sizes of 4 and 8. An independent, external third party performed the randomization prior to enrollment of the first participant and stored the allocation results in a sealed envelope. A second independent third party, working in a different department from the study team, also retained a copy of the randomization results. All study participants, field staff, and research team members were blinded throughout the trial. Only the two third parties holding the randomization results and the personnel responsible for labeling the treatments (who were not part of the field or research team) were unblinded.

## 2.6. Sample Size

Sample size calculations were based on the hypothesized effect size of 0.40 standard deviation (SD) between intervention and control groups on fetal whole brain volume at 36–38 weeks of

gestational age, and on Bayley-III cognitive scores, BERA indicators, and eye-tracking assessment indicators at 4–6 months of age ( $\alpha=0.05$  and  $1-\beta=0.80$ ). The original protocol assumed an effect size of 0.30 SD and a 20% attrition rate, resulting in a minimum sample size of 400 participants. However, due to recruitment challenges and increased loss to follow-up during the COVID-19 pandemic, which raised the anticipated attrition rate to 33.3% and constrained available funding, a protocol amendment was made. The target sample size was revised to detect a difference of 0.40 SD between groups, generally considered moderate and likely to be of clinical importance, resulting in a lowered estimated minimum sample size from 400 to 300 participants. Effect sizes between 0.30 and 0.40 SD were chosen based on prior findings: for Bayley-III domains, Cohen's  $d$  values in developmental cohorts and preterm interventions fall within this range; neuroimaging studies show between-group brain volume differences of approximately 0.30–0.50 SD in fetuses and neonates; and intervention-related physiologic/eye-tracking changes are typically described in similar effect size terms.

## 2.7. Study Procedures

Mothers in intervention and control groups consumed the supplements from the 2nd trimester of pregnancy until 6 months post-partum, regardless of their breastfeeding status. Outcomes assessments were performed at 36–38 weeks of gestational age for fetal brain volume and when children reaching the age of 4–6 months for Bayley-III, BERA, and eye-tracking assessments. Fetal brain growth was assessed using MRI, and infant development was evaluated using the Bayley-III for cognitive scores and other developmental scores, BERA for auditory function, and eye-tracking assessments, which included the IOWA and VPC tasks for attention and memory indicators.

### 2.7.1 Fetal brain MRI

Pregnant women were scanned in a supine position for fetal brain volume assessment on a 1.5-Tesla General Electric MRI with an acquisition time of approximately 30 minutes, depending on fetal motion. We used multi-planar repeated T2-weighted half Fourier acquisition single-shot turbo spin echo (T2wHASTE) sequences performed with a 2 or 4 interleaved acquisition; effective echo time of 100 and 120 ms; repetition time of 1400–2000 ms; variable field of view based on fetal and maternal size; 2–3 mm slice thickness; no inter-slice gap; 256×204, 256×256, or 320×320 acquisition matrices; and in-plane resolution of 1 mm.

Two independent trained physicians manually segmented brain regions of interest (i.e., whole brain, cerebrum, white matter, deep grey matter, cerebellum, and brainstem) with the supervision of a radiologist specialized in neurodevelopment; any discrepancies were reconciled with the radiologist. The outcomes derived from this assessment include:

- Whole brain volume in cm^3 (continuous).
- Cerebrum volume in cm^3 (continuous).
- White matter volume in cm^3 (continuous).
- Deep grey matter volume in cm^3 (continuous).
- Cerebellum volume in cm^3 (continuous).
- Brainstem volume in cm^3 (continuous).

Due to data quality issues, the myelination index could not be quantified as intended and was therefore excluded from further analysis.

### 2.7.2 Bayley Scales of Infant and Toddler Development, 3rd edition (Bayley-III)

Two trained psychologists conducted the Bayley-III assessment in a room with minimal distractions. The subscales included in this analysis were cognitive, receptive language, expressive language, fine motor, and gross motor. Before administering the assessment to study participants, we evaluated inter-rater agreement between the two assessors using data from three children, which resulted in a 56% agreement rate—considered moderate. Following this result, a group discussion was held to address the areas of disagreement. Due to pandemic-related constraints and time limitations, we were unable to conduct additional inter-rater reliability assessments.

The Bayley-III assessments were conducted twice between 4 and 6 months of age. For this analysis, we will use the first assessment for each child as the outcome measure to avoid potential influence from prior exposure to the Bayley-III assessment within a short interval. The outcomes derived from this assessment include:

- Bayley-III *Cognitive score*: Z-score converted raw score of Bayley-III cognitive subscale (continuous).
- Bayley-III *Cognitive composite score*: Score based on conversion of Bayley-III cognitive scaled score (continuous).
- Bayley-III *Receptive language score*: Z-score converted raw score of Bayley-III receptive language subscale (continuous).
- Bayley-III *Expressive language score*: Z-score converted raw score of Bayley-III expressive language subscale (continuous).
- Bayley-III *Language composite score*: Score based on conversion of combined Bayley-III receptive and expressive communication scaled scores (continuous).
- Bayley-III *Fine motor score*: Z-score converted raw score of Bayley-III fine motor subscale (continuous).
- Bayley-III *Gross motor score*: Z-score converted raw score of Bayley-III gross motor subscale (continuous).
- Bayley-III *Motor composite score*: Score based on conversion of combined Bayley-III fine and gross motor scaled scores (continuous).

We will use Bayley-III raw scores generated from each subscale based on the number of items passed and convert them into a z-score. Raw scores will also be converted into scaled scores based on normative data; the scale scores will be used to calculate cognitive, language and motor composite scores.

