## 5. ANALYSIS OF THE PRIMARY OUTCOME(S)

### 5.1. Main Analysis

We will perform all analyses after the last participant in the follow-up study has completed their visit. We will review the characteristics of the study sample as blinded cohort. First, we will use fake IDs and scrambled group code to write the script for analysis and create dummy tables and figures. Once the script, tables, and figures are ready, we will insert the correct IDs with blinded group code (e.g., A vs. B) and create the draft of the interpretation of the results for each case (e.g., if “A” is the Control group vs. if “A” is the Intervention group). We will finally reveal the group assignments after all authors have reviewed and approved the results for the primary outcomes. Unblinded analyses will be performed for secondary analyses, such as effect modification and subgroup analyses.

For all outcomes, the primary analysis to answer each objective will be a minimally adjusted model controlling only for child age at assessment and the randomization stratification factors (maternal education and municipality economic status). In secondary analyses, we will estimate adjusted parameters by including additional covariates—baseline characteristics, as well as post-enrollment and follow-up variables—in addition to those included in the primary analyses.

Unless otherwise specified, we will use two-sided confidence intervals at the 0.05 significance level for all analyses. For example, we are not powered to conduct subgroup/effect-modification analyses, so these secondary objectives will be exploratory and considered significant at the  $\alpha=0.10$  level. All hypothesis testing in this analysis plan is based on a two-sided superiority framework.

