#### 5.1.2 Baseline and fully adjusted analyses

We will also perform baseline and fully adjusted analyses with covariates for each outcome. First, we will perform bivariate analyses using the likelihood ratio test to test the association between the covariates with each outcome. Covariates with a p-value < 0.1 will be included in the adjusted analysis. Covariates with little variation in the study population (e.g., prevalence < 5%) will be

excluded. We will also evaluate the collinearity between potential covariates using the Variance Inflation Factor.

Potential covariates are listed below:

- Child sex: female or male
- Birth order: first-born or  $\geq$  second-born
- Municipality economic status: High or low
- Maternal height in centimeters
- Maternal pre-pregnancy BMI: BMI in  $\text{kg}/\text{m}^2$
- Maternal hemoglobin level at baseline in  $\text{g}/\text{L}$
- Maternal history of hypertension at baseline: With or without any history of hypertension
- Maternal age in years
- Maternal education: no education/incomplete primary/unknown, completed primary (6 years of formal education), completed secondary (9 years of formal education), completed greater than secondary
- Number of children under 5 yo in the household
- Number of household members
- Maternal marital status: monogamous marriage, polygamous marriage, or unmarried [single, divorced, widowed]
- Maternal occupation: housewife or working mother
- Paternal occupation: non-private sector and unemployed or private sector
- Monthly household expenditure in Indonesian Rupiah per month
- HOME inventory score (home environment)
- Screen time per day in minutes
- Staff members performing the assessment (for Bayley-III)

Two versions of adjusted analyses will be conducted as described below.

- Baseline adjusted model: This model will include covariates in minimally adjusted model and any of the following baseline covariates that are significantly associated at  $p < 0.1$  with the outcomes: child sex, birth order, maternal height, maternal pre-pregnancy BMI, maternal hemoglobin, maternal age, paternal age, paternal education, number of children under 5 yo in the household, number of household members, maternal marital status, maternal occupation, paternal occupation, household expenditure.

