**Table 2. Primary Estimands**

Primary Estimand for Primary Analysis					
Population	Treatment	Outcome	Summary Measure	Potential intercurrent events	Strategy for intercurrent event
ITT	Initially randomised treatment (Intervention v. Control) and any subsequent changes to treatment over treatment period	Whole fetal brain volume in cm  at 36–38 weeks of gestational age (continuous)	Minimally adjusted mean difference (95%CI) between treatment arms in whole brain volume in cm  , adjusted for gestational age at assessment and the randomization stratification factors (maternal education and municipality economic status)	
 
1. Treatment discontinuation without study withdrawal
 
2. Early study withdrawal
 
3. Treatment non-compliance (intermittent or partial treatment adherence not resulting in treatment discontinuation)
 
4. Dose adjustment
 
	Treatment Policy for all intercurrent events - all observed values will be used, regardless of whether or not the subject had experienced the intercurrent event
		Bayley-III Cognitive score at 4–6 months: Z-score converted raw score of Bayley-III cognitive subscale (continuous)	Minimally adjusted mean difference (95%CI) between treatment arms in Bayley-III cognitive score, adjusted for child age at assessment and the randomization stratification factors (maternal education and municipality economic status)		
		Bayley-III Cognitive composite score at 4–6 months: Score based on conversion of Bayley-III cognitive scaled score (continuous)	Minimally adjusted mean difference (95%CI) between treatment arms in Bayley-III cognitive composite score, adjusted for child age at assessment and the randomization stratification factors (maternal education and municipality economic status)		
		BERA absolute latencies at 4–6 months for wave I in ms (continuous)	Minimally adjusted mean difference (95%CI) between treatment arms in absolute latencies for wave I, adjusted for child age at assessment and the randomization stratification factors (maternal education and municipality economic status)		
		BERA absolute latencies at 4–6 months for wave III in ms (continuous)	Minimally adjusted mean difference (95%CI) between treatment arms in absolute latencies for wave III, adjusted for child age at assessment and the randomization stratification factors (maternal education and municipality economic status)		

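### The primary Bayley-III models leave out the assessor, so any constant scoring difference between the two psychologists stays in the residual: a modest loss of precision that is cheap to avoid

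*SAP*

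**What the plan says.** Section 2.7.2 states: "Two trained psychologists conducted the Bayley-III assessment". Before the study assessments, "we evaluated inter-rater agreement between the two assessors using data from three children", "which resulted in a 56% agreement rate", which the SAP calls moderate. Then "a group discussion was held to address the areas of disagreement", and because of pandemic and time limits "we were unable to conduct additional inter-rater reliability assessments".

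Section 5.1 states that the primary analysis for every outcome "will be a minimally adjusted model controlling only for child age at assessment and the randomization stratification factors". Section 5.1.1 lists the same terms: allocation group, child age, maternal education and municipality economic status. Table 2 repeats this for the first cognitive outcome: "Minimally adjusted mean difference (95%CI) between treatment arms in Bayley-III cognitive score, adjusted for child age at assessment and the randomization stratification factors". The cognitive composite row has the same adjustment. The Secondary Outcomes section and Table 3 carry the model over to the language and motor scores.

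Assessor appears once, in the list of potential covariates in section 5.1.2: "Staff members performing the assessment (for Bayley-III". That list serves the secondary adjusted analyses, and a covariate enters only if its bivariate association with the outcome has p<0.1.

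**The concern.** The Bayley-III is scored by a person, and the one agreement figure in the plan is not reassuring. If one psychologist scores consistently higher than the other, that gap becomes unexplained variation in a model without an assessor term. Two primary outcomes are affected, the cognitive score and the cognitive composite, together with the secondary language and motor scores.

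The plan itself treats assessor as relevant to this instrument, and listing it implies that the assessor's identity is available for each child. Section 2.4 says outcome assessors were blinded, so allocation should not influence who tested a child. Assessor is therefore not a plausible mediator, unlike the HOME score or screen time. The sample size also has little slack, so precision that can be had almost free is worth taking.

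**Working it through.** **Inputs from the SAP.** Section 2.6: effect 0.40 SD, alpha 0.05, power 0.80, anticipated attrition 33.3%, minimum total 300. Section 5.1: two-sided tests. Section 2.3: 1:1 allocation. Section 2.7.2: two assessors.

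**Assumed, because the SAP gives neither.** The constant difference between assessors is d within-assessor SDs (0.2, 0.5 and 0.8 are tried), and children are split 50:50 between assessors.

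**Step 1: the plan's own sample size.** n per arm = 2(1.960 + 0.842)²/0.40² = 98.1, so 99 per arm and 198 in total. 198/(1 − 0.333) = 297, which agrees with the stated 300. 300 less one third leaves 200 evaluable, or 100 per arm.

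**Step 2: variance left in the residual.** With share p of children seen by one assessor, omission adds p(1 − p)d² to a within-assessor variance of 1. At p = 0.5 this is d²/4.

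**Step 3: power.** The target effect is 0.40 total SD, where the total SD includes the assessor component. Without the assessor term, the noncentrality is 0.40 × √(100/2) = 2.828, and the two-sample t-test has power 80.4%. With the term, the residual SD falls by the factor √(1 + d²/4), so the standardised effect becomes 0.40 × √(1 + d²/4).

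| d | d²/4 | Standardised effect with assessor | Power with assessor | Gain over 80.4% (points) |
|---|---|---|---|---|
| 0.2 | 0.010 | 0.402 | 80.8% | 0.4 |
| 0.5 | 0.0625 | 0.412 | 82.7% | 2.3 |
| 0.8 | 0.160 | 0.431 | 85.8% | 5.4 |

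A cross-check takes 0.40 as a within-assessor SD and uses the normal approximation. Power with assessor is then 80.7%, and omission lowers it to 80.4%, 78.4% and 74.7%. This is the same loss seen from the other side.

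**Step 4: chance imbalance of assessor between arms.** The SD of the difference in assessor share between arms is √(2 × 0.25/100) = 0.071, so the unadjusted estimate shifts with SD 0.071d and variance 0.005d². The residual variance from Step 2 adds (d²/4) × (2/100) = 0.005d² to the variance of the treatment difference. These are the same quantity, so the imbalance must not be counted as a second loss.

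**Step 5: overlap with municipality.** If a fraction R² of the assessor indicator is explained by terms already in the model, the avoidable variance is (1 − R²)d²/4. For example, R² = 0.5 and d = 0.5 give 0.5 × 0.0625 = 0.031. The SAP does not say how children were assigned to assessors, so R² is unknown.

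**The case against.** The strongest reply is that nothing here is wrong. Allocation was randomised and assessors were blinded, so a model without assessor gives an unbiased estimate and a valid interval. One common model for all outcomes is a legitimate choice. That stands, and it limits the point to efficiency.

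A reader might infer that 56% agreement shows a large scoring gap that the model leaves uncorrected. The SAP does not support this. The figure comes from three children, predates the discussion held to resolve the disagreements, and does not describe agreement during the trial. Percent agreement also says nothing about direction: scattered disagreement can leave the two assessors' means equal, and an assessor term removes only a constant difference. Nor does the contrast with the ICC of 0.99 for BERA in six children (section 2.7.3) rank the instruments, because the two statistics are not comparable.

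A reader might also infer that chance imbalance between arms biases the estimate on top of the lost precision. Step 4 shows that the wider standard error already covers it.

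It can also be said that the p<0.1 screen in section 5.1.2 would usually pick assessor up. With 200 children split 50:50, it would do so about 97% of the time at d=0.5 and about 41% at d=0.2, where little is lost. This is fair as far as it goes. But the screen feeds only the secondary models. The primary cognitive result omits assessor whatever the screen finds.

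**Conclusion.** The point holds as a cheap improvement, not as an error in the plan. The SAP has no evidence that its two assessors score at the same level, regards assessor as a relevant Bayley-III covariate, and still leaves it out of the primary models.

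Under the stated assumptions, the gain is negligible at d=0.2, about 2 power points at d=0.5 and about 5 at d=0.8. Nothing in the SAP shows which value of d applies, and no passage supports a gap as large as 0.8. The gain shrinks if assessor partly follows municipality, and slightly if the split is uneven: at 70:30, power with assessor is 80.7%, 82.3% and 85.0%.

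**What to change.** In sections 5.1 and 5.1.1 and in the Bayley-III rows of Tables 2 and 3, pre-specify assessor (two levels) as a fixed effect in the minimally adjusted Bayley-III models, with no p-value screen. Report the model without assessor as a supporting result.

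The change should be fixed before the treatment groups are revealed. It needs SAP wording and one extra term, using a variable the plan already lists. The cost is one degree of freedom, about 0.3% on the standard error (√(198/197) = 1.0025), and a Bayley-III model that differs by one term from the model for the other outcomes.
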